# 9.3 Study Restrictions

Study restrictions are summarized in Table 9-1.

Table 9-1 Study VX15-984-001: Study Restrictions

	Study Period		
Restricted Medication/Food/Activity	Screening Period	Treatment Period	
Food Grapefruit/grapefruit juice Seville or blood oranges	None allowed within 7 days before the first dose of study drug	None allowed through the Safety Follow-up Visit	
Moderate and Strong CYP3A4 inhibitors or inducers	None allowed within 7 days before the first dose of study drug  None allowed through the Follow-up Visit		
Anti-emetics	Allowed for symptom management	Prophylactic use not allowed during Lead-in Period of Part A. Allowed beyond Lead-in Period in Part A and throughout Part B.	
Antidiarrheals	Allowed for symptom management	Prophylactic use not allowed during Lead-in Period and Cycle 1 of Part A. Allowed beyond Cycle 1 in Part A and throughout Part B.	
Hematopoietic growth factors	Not allowed	Prophylactic use not allowed during Lead-in Period and Cycle 1 of Part A. Allowed beyond Cycle 1 in Part A and throughout Part B.	

Note: Refer to the study reference manual for a complete list of medications prohibited in this study.

## 9.3.1 Additional Dietary Restrictions

• There are no restrictions on food and non-alcoholic beverages, except restrictions mentioned in Table 9-1.

## 9.3.2 Activity

- Subjects will abstain from strenuous exercise (e.g., heavy lifting, weight training, and aerobics) for at least 48 hours before each blood collection for clinical laboratory tests. Walking at a normal pace will be permitted.
- Subjects should avoid prolonged or intense sun exposure, sunlamps, and tanning beds. Use of sunscreen, clothing, and eyewear that decrease sun exposure is recommended.

#### 9.4 Prior and Concomitant Medications

In vitro drug metabolism studies suggest that VX-984 is a substrate of CYP3A4 and its systemic exposure may be affected by concomitant medications that are moderate or strong CYP3A4 inhibitors or inducers. Restrictions for prior and concomitant medications that are moderate or strong inhibitors and inducers of CYP3A4 are provided in the Study Reference Manual. Based upon in vitro data, VX-984 is a weak to moderate inhibitor of CYP3A. Therefore, use of drugs that are metabolized mainly by CYP3A and have a low therapeutic

index is not allowed in the study. Investigators should use standard precautions when prescribing medications, as with any novel therapeutic for which there is limited clinical experience.

- Subjects will abstain from concomitant medications as described in Table 9-1. If a prohibited medication is considered medically necessary for a subject, the subject will be withdrawn from the study
- Subjects should not receive prophylactic treatment with hematopoietic growth factors and antidiarrheal medications during the Lead-in Period and Cycle 1 of Part A. These treatments may be used to specifically address subject symptoms, per institutional practice, as long they adhere to restrictions listed in Table 9-1
- The Investigator should refer to the package inserts for PLD for guidance on prohibited medications during treatment with this agent. Subjects should not use nephrotoxic or ototoxic medications from 7 days before the first dose of study drug through the Safety Follow-up Visit. Inadvertent or short-term use while in the study will not cause a subject to be ineligible
- Medications taken from 28 days before the first dose of study drug will be documented as
  a prior medication. Medications taken after the first dose of study drug through the end of
  the study will be documented as concomitant medications. All medications must be
  recorded with indication, route of administration, and start and stop dates of
  administration. All subjects will be questioned about concomitant medication at each
  clinic visit.

### 9.5 Removal of Subjects

Subjects may withdraw from the study at any time at their own request. Subjects may be withdrawn from study drug treatment at any time at the discretion of the Investigator or EMD Serono Research & Development Institute (the Sponsor) for safety, behavior, noncompliance with study procedures, or administrative reasons. If a subject has been withdrawn from study drug treatment, the subject will continue to be followed, provided the subject has not withdrawn consent.

If a subject does not return for a scheduled visit, reasonable effort will be made to contact the subject. In any circumstance, reasonable effort will be made to document subject outcome. The Investigator will inquire about the reason for withdrawal, request that the subject return all unused investigational product(s), request that the subject return for a Safety Follow-up Visit, if applicable (see Section 8.1.5), and follow up with the subject regarding any unresolved AEs.

If the subject withdraws consent for the study, no further evaluations will be performed and no additional data will be collected. The Sponsor may retain and continue to use any data collected before such withdrawal of consent.

Subjects may be discontinued from study drug for toxicity or lack of efficacy, as specified in Section 8.1.3.

### 9.6 Replacement of Subjects

In Part A, subjects who withdraw or are withdrawn from treatment for reasons other than DLT before the Cycle 1 Day 28 assessment and who have not had the minimum exposure to study drugs described in Subject Evaluability will be replaced. Subjects who withdraw or are withdrawn from treatment beyond Cycle 1 will not be replaced.

For Part B, subjects who discontinue for reasons other than disease progression or are non-evaluable for efficacy analysis may be replaced. Subjects who discontinue for disease progression before the completion of Cycle 1 may also be replaced.

#### 10 STUDY DRUG ADMINISTRATION AND MANAGEMENT

#### 10.1 Preparation and Dispensing

Study drug may be dispensed only under the supervision of the Investigator or an authorized designee and only for administration to the study subjects.

Study drug will be supplied to sites as individual dosing containers of VX-984 adipic acid cocrystal powder (drug product intermediate) with additional adipic acid.

The final suspension will be prepared using a vehicle containing 0.5% methylcellulose, 0.1% sodium benzoate, 0.1% benzoic acid, and adipic acid (amount varies with dose). Details of dose preparation, including constitution, will be given in a separate document (Formulation Preparation Instructions).

Individual dose concentrations of VX-984 will be bracketed between 8 mg/g and 50 mg/g in the suspending vehicle.

The subjects will be provided with 3 containers per dose:

- VX-984 adipic acid cocrystal powder,
- dosing vehicle, and
- vehicle to be used as rinsate.

All 3 containers will be labelled appropriately for easy administration.

### 10.2 Criteria for Study Drug Administration

When clinical chemistry and/or hematology laboratory testing is required as described in the Schedule of Assessments (Table 3-1, Table 3-2, and Table 3-3) before administration of chemotherapy or VX-984, the laboratory criteria specified in Table 10-1 must be met before dosing. To facilitate timely administration of study drug, this laboratory testing may be performed up to 3 days before dosing.

Cycle 1, Day 1 **Laboratory Parameter** Day 1 of Subsequent Cycles Hemoglobin  $\geq 9.0 \text{ g/dL}$  $\geq 7.0 \text{ g/dL}$ (if asymptomatic) Absolute neutrophil value  $\geq 2.5 \times 10^{9}/L$  $\geq 1.5 \times 10^{9}/L$  $\geq 100 \times 10^9/L$ Platelet count  $\geq 125 \times 10^{9}/L$ AST, ALT  $< 2 \times ULN$  $\leq 2 \times ULN$ Estimated glomerular filtration > 50 mL/min > 45 mL/min (if no more than 20% decrease from prior cycle)  $\leq 1.5 \times ULN^a$ Total bilirubin (serum)  $\leq 1.5 \times ULN^a$ 

Table 10-1 Laboratory Values Required for Administration of Chemotherapy or VX-984

#### 10.3 Administration

#### VX-984, On-site and In-home:

When on-site at the clinic, subjects may receive either the suspension already mixed or subjects will prepare their dose in the presence of a nurse or other authorized designee. Subjects will also receive a rinsate container containing vehicle.

Steps for mixing and consuming the study drug are as follows:

- The contents of the dosing vehicle will be added to the VX-984 adipic acid cocrystal powder. The container will be sealed, and the contents will be shaken to mix and consumed immediately
- The contents of the second vehicle container will be used as a rinsate and added to the residual material. The container will be sealed, and the contents will be shaken to ensure that no powder is left behind. The contents will be consumed immediately.

For in-home administration by the subject, a kit will be provided that contains 3 containers per dose needed for in-home administration. For example, if a subject will take the next 2 doses at home, a total of 6 containers will be provided.

#### PLD, On-site:

PLD, supplied as single use vial: 20 mg/10 mL or 50 mg/25 mL. PLD doses up to 90 mg will be diluted in 250 mL of 5% Dextrose Injection, USP before administration. PLD doses exceeding 90 mg will be diluted in 500 mL of 5% Dextrose Injection, USP before administration. Diluted PLD must be refrigerated at 2° to 8°C and administered within 24 hours.

The Investigator should refer to the DOXIL®/CAELYX® label for administration guidelines of PLD. Precautionary preparations should be made to prepare for serious and sometimes life-threatening infusion-related reactions that may occur most commonly during the first infusion of PLD, but may also occur in subsequent cycles. Acceptable window for infusion:  $\pm$  25% of the planned infusion time.

EMD Serono Research & Development Institute Document No. CCI
Object No. CCI

Unless subject has known or suspected Gilbert's syndrome

## 10.4 Method of Assigning Subjects to Treatment Groups

This is an open-label study.

## 10.5 Dose Modification and Dose Delay for Toxicity

#### Part A:

Doses of VX-984 or PLD may be reduced beyond Cycle 1 for toxicity using the following guidelines:

- For Grade 4 neutropenia or thrombocytopenia: Delay dosing until absolute neutrophil count  $\geq 1500$  and platelets  $\geq 75000$ . The dose of VX-984 will be reduced to previous tolerated dose level and PLD will be reduced by 25% when dosing resumes
- For HFS and stomatitis, modify PLD doses according to DOXIL package insert
  - For Grade 1 HFS and stomatitis: if no previous Grade 3 or 4 HFS, no dose adjustment. If previous Grade 3 or 4 HFS, delay dose for up to 2 weeks, then decrease PLD dose by 25%
  - o Grade 2, 3 and 4 HFS and stomatitis: delay dosing up to 2 weeks or until resolved to Grade 0 or 1, then decrease PLD dose by 25%. Discontinue treatment if no resolution after 2 weeks
- For other Grade 3 non-hematologic toxicity: Do not dose until recovered to Grade < 2, then reduce the dose of VX-984 to the previous tolerated dose level and PLD by 25%
- For Grade 4 non-hematologic toxicity: Do not dose until recovered to Grade < 2, then reduce the dose of VX-984 to the previous tolerated dose level and PLD by 25% or discontinue treatment
- For dose delays of more than 1 week due to toxicity: Reduce VX-984 dose to the previous tolerated dose level
- For dose delays of more than 4 weeks due to drug-related toxicity other than HFS and stomatitis: Discontinue treatment, unless in the opinion of the Investigator, the subject is experiencing clinical benefit and it is in their best interest to continue treatment. For these subjects treatment may continue at a reduced dose, at the discretion of the Investigator and sponsor.

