<sup>j 12-lead ECG will be measured on Day 1 up to 60 minutes before administration of PLD. ECG will be measured on Day 2 only during Cycle 1 and will be measured up to 60 minutes before administration of VX-984, and 2 and 4 hours (± 60 minutes) after administration of VX-984.

<sup>k To facilitate timely administration of study drug on Day 1, safety lab samples may be collected up to 3 days before Day 1. If safety lab samples are collected before Day 1, they should be recorded as corresponding to Day 1.

<sup>1 Female subjects of childbearing potential only.

<sup>m For Part A: For Cycle 1, subjects will receive VX-984 in the clinic on Days 2 and 4; and at home on Day 3. After Cycle 1, subjects will be instructed to take all VX-984 doses at home per instructions provided in Section 10.3.

For Part B: For Cycle 1, subjects will receive VX-984 in the clinic on Day 4 or the day subjects come in for PK assessment; and at home on Days 2 and 3. After Cycle 1, subjects will be instructed to take all VX-984 doses at home per instructions provided in Section 10.3.

<sup>n Cycle 1 only. VX-984 plasma PK samples will be collected on Day 2 before dosing (0 hour) and at 0.5, 1, 2, and 4 hours after dosing; and on Day 4 before dosing (0 hour) and at 0.5, 1, 2, 4, 8, and 24 hours (Day 5) after dosing.

Ocycle 1 only. PLD plasma PK samples will be collected on Day 1 before beginning of infusion (BOI) and at 1, 2, 4, 6, 24 hours (Day 2), 72 hours (Day 4) and 96 hours (Day 5) after BOI.

<sup>p Cycle 1 only. VX-984 plasma PK samples will be collected on Day 4 before dosing (0 hour) and at 0.5, 1, 2, 4, and 8 hours after dosing. PK sampling may occur on Days 2 or 3 if subjects are unable to come to the clinic on Day 4. PK samples are required from a minimum of 20 subjects.

Table 3-3 Study VX15-984-001: VX-984 and PLD Combination Therapy and Follow-up (Parts A and B)									
Event/Assessment	Day 1	Day 2	Day 3	Day 4	Day 5	Day 8	Day 15	Follow	w-up a
During Each Cycle (Except as Noted)								28 days (± 7 days)	5 weeks (± 1 week)
Part B PLD (Plasma PK collection)				X q					
Exploratory Assessments									

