#### Part B

- Subjects with histologically confirmed advanced primary endometrial cancer (locally advanced and incurable endometrial cancer that has been treated with surgery and/or radiation or is ineligible for such treatment), or recurrent or metastatic endometrial cancer, and
- Completed 1 line of chemotherapy treatment with a platinum-containing regimen in the advanced setting
- 3. Measurable disease according to RECIST criteria (Version 1.1)
- 4. WHO performance status of 0 or 1
- 5. Life expectancy of at least 12 weeks

- 6. Hematological and biochemical indices within the ranges shown below at screening. These values must be confirmed within 3 days before the first day of dosing, before study drug administration:
  - a. Hemoglobin:  $\geq 9.0 \text{ g/dL}$
  - b. Absolute neutrophil count:  $\geq 2.5 \times 10^9/L$
  - c. Platelet count:  $\geq 125 \times 10^9/L$
  - d. Serum bilirubin:  $\leq 1.5 \times \text{upper limit of normal (ULN)}$
  - e. ALT, AST:  $\leq 2 \times (ULN)$
  - f. Estimated glomerular filtration rate: ≥ 50 mL/min
  - g. Prothrombin time:  $< 1.25 \times ULN$  unless on anticoagulant therapy and discussed with the medical monitor

In addition, there should not be other clinically significant metabolic or hematologic abnormalities that are uncorrectable or that require ongoing, recurrent pharmacologic management (except subjects who are receiving potassium, magnesium, or other supplementation for an otherwise controlled condition)

- 7. Normal left ventricular ejection fraction on screening assessed by transthoracic echocardiogram or MUGA scan
- 8. Subject will sign and date an informed consent form (ICF)
- 9. Willing and able to comply with scheduled visits, treatment plan, study restrictions, laboratory tests, contraceptive guidelines, and other study procedures.

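### In Part A, Section 10.5 lets dosing resume after Grade 4 neutropenia or thrombocytopenia at a platelet count below the one Table 10-1 requires on Day 1 of later cycles, and nothing says which governs

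*Protocol*

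**What the plan says.** Two current sections of the protocol set counts that must be reached before a Part A subject is dosed again.

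- **Section 10.5, Part A.** The bullet begins "For Grade 4 neutropenia or thrombocytopenia: Delay dosing until absolute neutrophil count" and continues with a neutrophil value of at least 1500 and a platelet value of at least 75000, without units. It then gives the doses to be used afterwards: VX-984 goes back to the previous tolerated level, and "PLD will be reduced by 25% when dosing resumes". The bullet therefore describes actual resumption.
- **Section 10.6.** After an interruption for Grade 3 or higher toxicity beyond Cycle 1, it refers to Section 10.5 for how treatment may resume. It does not mention Table 10-1.
- **Section 10.2 and Table 10-1.** Where the schedule calls for laboratory tests before chemotherapy or VX-984, "the laboratory criteria specified in Table 10-1 must be met before dosing". The table has a column for Cycle 1 Day 1 and one headed "Day 1 of Subsequent Cycles". For later cycles it requires neutrophils of at least 1.5 x 10^9/L and platelets of at least 100 x 10^9/L.
- **Section 8.1.2.1.1.** It points to Section 10.2 for the Day 1 dosing criteria in Cycle 1 and afterwards, so the table applies at the start of every Part A cycle.

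Sections 10.2 and 10.5 do not refer to each other. Neither exempts resumption after toxicity or says which prevails.

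**The concern.** The two rules meet at the same decision: whether to give Day 1 treatment of a later cycle to a Part A subject who is recovering from Grade 4 neutropenia or thrombocytopenia. On neutrophils they ask for the same count. On platelets they do not. An investigator who follows Sections 10.6 and 10.5 may treat at a count at which one who follows Section 10.2 must wait.

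What is at stake is subject safety and uniform practice across sites at a sensitive moment, the first dose after a Grade 4 blood count. The choice also sets the length of the delay, which counts towards the rule in Sections 8.1.3 and 10.5 on drug-related delays of more than 4 weeks. Part A is the part affected, and it is the only part the SAP still covers (SAP Section 7).

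**Working it through.** No sample size, power or error rate is involved, so this is a comparison of thresholds.

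**1. Put both rules in the same units.** Section 10.5 prints no units; per microlitre is an assumption. One cell per microlitre is 10^6 per litre, so:
- neutrophils: 1500 x 10^6/L = 1.5 x 10^9/L;
- platelets: 75000 x 10^6/L = 75 x 10^9/L.

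The converted neutrophil value equals the later-cycle value in Table 10-1 exactly, which supports the assumption.

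**2. Place the platelet figures in Table 10-1.** The table is broken in the text available, but its only platelet values are 125 and 100 x 10^9/L. Inclusion criterion 6c requires 125 x 10^9/L at entry, so 125 belongs to Cycle 1 Day 1 and 100 to later cycles. The existence of the conflict does not depend on this, since both values exceed 75. Only the size of the gap does: 100 - 75 = 25 x 10^9/L as placed here, or 125 - 75 = 50 x 10^9/L if the columns were reversed.

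**3. Compare, for Day 1 of a later cycle.**

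| | Section 10.5 (Part A) | Table 10-1, later cycles | Agree? |
|---|---|---|---|
| Neutrophils, x 10^9/L | at least 1.5 | at least 1.5 | yes |
| Platelets, x 10^9/L | at least 75 | at least 100 | no, gap 25 |

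**4. Apply both rules by count.**
- Neutrophils below 1.5: both rules bar dosing, whatever the platelets.
- Neutrophils at least 1.5, platelets below 75: both bar dosing.
- Neutrophils at least 1.5, platelets from 75 to under 100: Section 10.5 is met and Table 10-1 is failed.
- Neutrophils at least 1.5, platelets 100 or more: both are met.

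**5. Check that the two rules really meet.** Table 3-3 schedules hematology during each cycle on Days 1, 8 and 15, with PLD on Day 1 and VX-984 on Days 2 to 4. Its laboratory footnote is tied to the same dose: "To facilitate timely administration of study drug on Day 1, safety lab samples may be collected up to 3 days before Day 1". A Grade 4 count found on Day 8 or 15 is therefore followed next by Day 1 of a later cycle, where Table 10-1 applies. If both rules had to be satisfied there, 100 would always decide and 75 never would.

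**The case against.** The strongest reply is that the rules are cumulative. Section 10.5 introduces its bullets as guidelines and sets a minimum delay; it does not waive Table 10-1, whose wording is mandatory. A site can wait out the delay and then apply the Day 1 check, so no subject receives contradictory orders. This reading is possible, but the protocol does not state it. Section 10.6 sends the reader to Section 10.5 alone, and the bullet is itself worded as an instruction. On this reading the printed platelet figure also has no effect on any Day 1 dose. Either the two thresholds conflict or one is inoperative, and both call for correction.

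A reader might infer more than the documents support:

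- **That the platelet figure is a mistake.** Matching neutrophil values do not show this. Section 10.5 concerns resumption at reduced doses, Table 10-1 is a general gate, and the documents do not say whether the difference was intended.
- **That all later-cycle dosing, or every subject with platelets in the gap, is affected.** The table column concerns Day 1, and no hematology is scheduled on Days 2 to 4. The conflict also needs Part A, a preceding Grade 4 neutropenia or thrombocytopenia, and adequate neutrophils.
- **That the delay changes the dose through the rule on delays of more than 1 week.** That rule returns VX-984 to the previous tolerated level, which the Grade 4 bullet already requires whatever the delay.
- **That the delay changes DLT status and so the MTD.** Under Table 8-2, Grade 4 thrombocytopenia is already a DLT, as is Grade 4 neutropenia lasting more than 7 days. The criterion on interruption beyond 14 days could add something only after shorter Grade 4 neutropenia. MTD estimation uses Cycle 1 DLTs (Section 12.3.3.1), while the Section 10.5 guidelines concern dosing beyond Cycle 1.

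**Conclusion.** The point holds as an internal inconsistency limited to platelets. In Part A, on Day 1 of a later cycle after Grade 4 neutropenia or thrombocytopenia, a subject with neutrophils of at least 1.5 and platelets from 75 to under 100 x 10^9/L meets Section 10.5 and fails Table 10-1. The gap is 25 x 10^9/L. This measures the distance between two thresholds, not the number of subjects; the documents give no frequency for such cases.

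The conclusion rests on two stated assumptions: that Section 10.5 is in cells per microlitre, and that 100 x 10^9/L is the later-cycle value in Table 10-1. It should be corrected because it concerns retreatment safety and the correction is simple. It is not shown to affect the MTD or any planned analysis.

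**What to change.** Reconcile Section 10.5 (Part A) and Section 10.6 with Section 10.2 and Table 10-1, so that a single platelet criterion governs resumption on Day 1 of a later cycle. Alternatively, state which section takes precedence after Grade 4 neutropenia or thrombocytopenia. If the two are meant to be cumulative, say so and say what the Section 10.5 platelet figure is for. Print units in Section 10.5 and add a cross-reference in each direction. Which figure applies is for the sponsor and investigators to settle; this review takes no view.

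The cost is a clarification of about one line in the protocol, communicated to sites. No design, sample size or SAP change follows from it.

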#### Part B:

For drug-related toxicity, the following modifications of drug dose and schedule will be made:

- In case of non-hematologic Grade 3 or higher toxicity (excluding fatigue or nausea/vomiting/diarrhea adequately managed by supportive care), treatment will be interrupted and may be resumed when all toxicities have returned to Grade < 2, at the discretion of the Investigator
- For the following hematologic toxicities, once the toxicity has returned to Grade < 2, dosing can be resumed with a 25% reduction in VX-984 dose. If, after 25% reduction of

VX-984 dose, any of the below drug-related hematologic toxicities are subsequently observed, then, the dose of PLD will be reduced by 25%

- o Grade 4 thrombocytopenia
- Febrile neutropenia (growth factor support, per site protocol, may be used in lieu of dose reduction)
- o Grade 4 neutropenia lasting more than 7 days (growth factor support, per site protocol, may be used in lieu of dose reduction)
- For the following non-hematologic toxicities, once the toxicity has returned to Grade < 2, dosing can be resumed at a lower dose of chemotherapy. PLD dose will be reduced by 25%. If any of the below drug-related toxicity is subsequently observed with the reduced dose of chemotherapy, VX-984 dose will be reduced by 25%
  - o Grade 3 non-hematologic toxicity (Except for fatigue or nausea, vomiting, or diarrhea adequately controlled by medication)
  - o Any non-hematologic toxicity requiring dose delay of more than 2 weeks.
- For Grade 4 non-hematologic toxicity, treatment will be interrupted and may be resumed at a lower dose when toxicity has returned to Grade < 2 or subjects may be removed from the study. VX-984 dose will be reduced by 25%. In addition, the PLD dose will be reduced by 25%
- For HFS and stomatitis, modify PLD doses according to DOXIL package insert
  - For Grade 1 HFS and stomatitis: if no previous Grade 3 or 4 HFS, no dose adjustment. If previous Grade 3 or 4 HFS, delay dose for up to 2 weeks, then decrease PLD dose by 25%
  - o Grades 2, 3 and 4 HFS and stomatitis: delay dosing up to 2 weeks or until resolved to Grade 0 or 1, then decrease PLD dose by 25%. Discontinue treatment if no resolution after 2 weeks
- For dose delays of more than 4 weeks due to drug-related toxicity other than HFS and stomatitis: Discontinue treatment, unless in the opinion of the Investigator, the subject is experiencing clinical benefit and it is in their best interest to continue treatment. For these subjects treatment may continue at a reduced dose, at the discretion of the Investigator and sponsor.

If any toxicity not described above results in delay in dosing in any part of the study and the subject may be benefitting from therapy, then at the discretion of the Investigator, the dose of VX-984 or chemotherapy may be reduced by 25%.

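### Section 10.5 does not say which rule governs hand-foot syndrome and stomatitis where their own bullet overlaps the general non-hematologic bullets, and the two differ on stopping versus resuming.

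*Protocol*

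**What the plan says.** The HFS and stomatitis bullet in Section 10.5 is worded almost identically in Parts A and B. It addresses PLD doses and refers to the package insert. For Grades 2 to 4 it says "delay dosing up to 2 weeks or until resolved to Grade 0 or 1". The PLD dose is lowered by a quarter at that point, and the bullet closes with "Discontinue treatment if no resolution after 2 weeks". VX-984 is not mentioned.

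The general bullets around it are as follows.

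- Part B, trigger: "Any non-hematologic toxicity requiring dose delay of more than 2 weeks". Action: "once the toxicity has returned to Grade < 2, dosing can be resumed at a lower dose of chemotherapy", with PLD cut by 25%. The same action covers Grade 3 non-hematologic toxicity, with exceptions only for fatigue and for controlled nausea, vomiting or diarrhea. If such a toxicity recurs on the reduced PLD dose, VX-984 is cut by 25%.
- Part B, Grade 4 non-hematologic: dosing may resume below Grade 2 with both drugs cut by 25%, or the subject may be removed.
- Part A, Grade 4 non-hematologic: no dosing until below Grade 2, then VX-984 goes to the previous tolerated level and PLD is cut by 25%, or treatment stops.
- Part A, delay: "For dose delays of more than 1 week due to toxicity: Reduce VX-984 dose to the previous tolerated dose level".

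HFS and stomatitis are explicitly excluded in only two kinds of place. One is the rule for delays beyond 4 weeks (Section 8.1.3 and both parts of Section 10.5). The other is the Part A Grade 3 bullet, which says it concerns other toxicity and comes straight after the HFS bullet. None of the general bullets listed above excludes them.

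**The concern.** HFS and stomatitis are non-hematologic toxicities, so a general bullet without an exclusion reaches them on its face. Where the authors wanted an exclusion they wrote one, so a site could take its absence elsewhere as deliberate. Another site could assume that the named-toxicity bullet overrides the rest. For the same event, the two sites could reach different decisions on stopping and on which drug to reduce.

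Section 10.6 refers sites to Section 10.5 for resumption after Grade 3 or higher toxicity, so this is the text they would use. The SAP then reports the results by drug: dose intensity and relative dose intensity (Section 13), TEAEs leading to reduction or permanent discontinuation of VX-984, PLD, either or both (Section 15.2.2), and discontinuations by reason (Section 10.1). Identical events could fall in different rows of those tables.

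**Working it through.** The plan states no figure on this point to reproduce. The check applies each bullet, as worded, to the same hypothetical subject. Days count from the start of the dose delay.

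| Case | HFS/stomatitis bullet | General bullet | Result |
|---|---|---|---|
| 1. Part B, Grade 2–4, unresolved at day 14, Grade 1 at about day 21 | Discontinue | Over-2-week bullet: may resume, PLD −25% | Conflict: stop vs resume |
| 2. Part A, Grade 4, unresolved at 2 weeks, recovers later | Discontinue | Grade 4 bullet: resume with both drugs reduced, or stop; no 2-week limit | Conflict where the site resumes |
| 3. Part B, second Grade 3 HFS after a PLD reduction, resolved within 2 weeks | PLD −25% again | VX-984 −25% | Different drug cut |
| 4. Part A, Grade 2 HFS, resolved at day 10 | PLD −25% | Over-1-week bullet: VX-984 to previous level | Ambiguous; both can be applied |
| 5. Either part, Grade 4 stomatitis, resolved by day 10 | PLD −25% | If dosing resumes, both drugs reduced | Ambiguous for VX-984 |
| 6. Part B, first Grade 3 HFS, resolved within 2 weeks | PLD −25% | PLD −25% | No conflict |
| 7. Part A, Grade 3 HFS, resolved within 1 week | PLD −25% | Grade 3 bullet excludes HFS | No conflict |

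**Case 1.** Recovery to Grade 0 or 1 and recovery to below Grade 2 are the same threshold on an integer scale. The two bullets therefore differ only in what happens after 2 weeks: permanent discontinuation, against continuation at 1 − 0.25 = 75% of the PLD dose.

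**A third route.** Table 8-2 counts a drug-related toxicity that interrupts treatment for more than 14 days as a DLT. Section 8.1.3 lets a subject with a reversible, non-life-threatening DLT and possible clinical benefit resume below Grade 2. It sets no 2-week limit and does not exclude HFS or stomatitis.

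**Case 3.** Assume PLD starts at 40 mg/m² and each 25% is taken off the current dose. After the first event PLD is 40 × 0.75 = 30 mg/m². At the second event:

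- HFS bullet alone: PLD 30 × 0.75 = 22.5 mg/m², VX-984 at 100%.
- General bullet alone: PLD 30 mg/m², VX-984 at 75%.
- Both together: PLD 22.5 mg/m², VX-984 at 75%.

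If 25% means 25% of the starting dose each time, 22.5 becomes 40 − 2 × 10 = 20 mg/m².

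**Case 4.** On the provisional levels of Table 8-1, one VX-984 step down is:

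- 240 to 120 mg: 1 − 120/240 = 50%
- 480 to 240 mg: 1 − 240/480 = 50%
- 720 to 480 mg: 1 − 480/720 = 33%

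The alternative is no VX-984 cut if a site treats the HFS bullet as complete. At 120 mg the step is undefined, because levels 1 and −1 both use 120 mg.

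**The case against.** A reader might infer that the plan orders VX-984 both to be reduced and not to be reduced. The documents do not support that. The HFS bullet addresses PLD only and never says that VX-984 stays unchanged. In cases 4 and 5 a site can follow both bullets without breaching either. That part is an ambiguity inferred from silence. In case 3, too, neither bullet forbids the other's cut, although following both gives a third dosing outcome.

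The stop-versus-resume conflict can also be overstated. The Part B general bullet permits resumption and does not require it, and the Grade 4 bullets allow stopping as well. A site that discontinues breaches nothing. What remains is that a site that resumes is within one bullet and against the other.

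The structure gives some support to the view that the HFS bullet was meant to stand alone: excluding HFS and stomatitis from the over-4-week rule is natural if they have already been dealt with at 2 weeks. But no sentence says so, and the exclusions are uneven. The Part A Grade 3 bullet carries one and the Grade 4 bullet directly after it does not. The package insert to which the HFS bullet defers was not available for this check.

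A reader might also infer that dose finding is compromised. It is not. The Part A bullets are guidelines for reductions beyond Cycle 1, and the MTD rests on Cycle 1 DLTs (Protocol Section 12.3.3.1, SAP Section 15.1). SAP Section 7 states that Part B will not be pursued, so cases 1 and 3 have no planned Part B analysis to affect.

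**Conclusion.** The concern holds as a missing precedence rule with one firm conflict. HFS or stomatitis unresolved at 2 weeks is to be discontinued under its own bullet. The Part B over-2-week bullet permits resumption, and so does the Part A Grade 4 bullet. The recurrent Grade 3 case in Part B is a second divergence, on which drug is cut. Whether VX-984 is also reduced (Part A delay over 1 week; Grade 4 in both parts) is an ambiguity.

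Per event, the firm conflict is permanent discontinuation against continued treatment: at 75% of PLD in Part B, and with both drugs reduced in Part A. The Part A VX-984 ambiguity is 0% against 33% or 50% on the provisional levels above 120 mg. The documents give no expected frequency of these delays, so the number of subjects affected is unknown. The effect is confined to post-Cycle 1 exposure, dose-reduction and discontinuation summaries, and with Part B dropped the remaining practical weight is in Part A. The conclusion assumes that HFS and stomatitis count as non-hematologic, which the wording of the Part A Grade 3 bullet implies.

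**What to change.** Reconcile Section 8.1.3 and both parts of Section 10.5 so that exactly one stated rule applies to HFS and stomatitis at each grade and delay length. Either a precedence sentence or an explicit exclusion in every general bullet that is not meant to cover them would do this. The text should state the action for VX-984 as well as for PLD, including no change where that is intended, and should say how resumption after a DLT under Section 8.1.3 fits with the 2-week limit. Which clinical rule to keep is for the sponsor. The cost is a wording change, with no added data, visits or subjects.
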